The study design was developed over a series of in-person meetings; roles and responsibilities for all research personnel have been explicitly identified, as well as a timeline of activities. [name] has been informed of the protocol and specific research-related duties and functions and will be supervised by [name] [name] throughout all phases of the study. Prior to enrolling participants, we will hold regular lab meetings (weekly emails, Zoom meetings) to review specific roles.

6.5. Explain why you do not need additional qualified staff, other than those listed in Sections 1 and 6, to conduct your study.

[name], [name], [name], and [name] will be fully responsible for the primary study. Given its simplicity of data collection procedure, consent form, anthropometric and blood draw, will be collected by these four investigators.

7. Characteristics of Participants

7.1. Approximate Number of Participants to be recruited: 50

7.2. Age Range of Participants: 14-30

7.3. If your age range includes an upper limit, justification must be provided: The ages of 14-30 are considered adolescents and young adulthood and has recently been recognized as a critical time period for the development of obesity related diseases such as CVD and T2D. It is during this life stage that young adults begin to establish health behavior patterns (e.g., physical activity and eating habits) that last into late adulthood. Therefore, it may be beneficial to develop strategic ways specifically targeting emerging young adulthood to delay the onset of obesity related diseases.

If not, please indicate No.

7.4. Does this study target a vulnerable population such as children, those with decisional impairments, or prisoners? Does the study target a specific population, gender, social, or ethnic group?

No. (Skip to 7.5)

Yes. If yes, answer 7.4.1. and 7.4.2. below.

7.4.1. If yes, check all that are targeted/vulnerable populations and when appropriate provide a copy of the required form. *The forms can be found on the IRB Website under Special Populations: <http://researchintegrity.syr.edu/human-research/forms/>

- Children/minors - *Requires additional form*
- Decisionally impaired - *Requires additional form*
- Prisoners - * Requires additional form*
- Pregnant women - *Requires additional form*
- Legally restricted, non-prisoner
- Educationally disadvantaged
- Economically disadvantaged
- Elderly/aged
- Other, specify: _____

***NOTE*:** These additional forms can be found on the IRB Website (under Special Populations): <http://researchintegrity.syr.edu/human-research/forms/>

7.4.2. Explain the rationale for using this particular group(s): _____

7.5. List all study specific inclusion/eligibility criteria (e.g.-gender, age range, population characteristics, location, etc.):

A) Adolescents (age 14-17 years old with sex- and race-specific BMI percentile $\geq 85^{\text{th}}$) and young adults with overweight and obesity (age 18 to 30 years old with BMI $\geq 25 \text{ kg/m}^2$)

B) Free from the following chronic medical conditions: heart disease, arrhythmias, diabetes, thyroid disease, bleeding disorder, history of pulmonary disease, hypertension, hepatorenal disease, musculoskeletal disorder, neuromuscular/neurological disease, autoimmune disease, cancer, peptic ulcers, anemia, or chronic infection (HIV).

C) Have not taken any heart, pulmonary, thyroid, anti-hyperlipidemic, hypoglycemic, anti- hypertensive, endocrinologic (e.g., thyroid, insulin, etc.), emotional/psychotropic (e.g., Prednisone, Ritalin, Adderall), neuromuscular/neurological, or androgenic medications (anabolic steroids).

D) Live in the greater Syracuse area.

E) Does not have a pacemaker.

F) For females: are not pregnant or lactating.

We will explain details of the health conditions for the participants to make sure they understand each health condition completely. We will also examine their body composition before we determine whether they are qualified to participate in the study. During the study, if participants have concerns regarding their health conditions, they are free to refuse to participate, or to withdraw from the study at any time. If there is concern about their medical safety, we may recommend participants seek medical attention. During the initial visit, physicians are not being consulted.

Inclusion criteria will be monitored by [name] [name] and [name], when they contact him and communicate about the study procedure via email and/or phone (i.e., potential eligible participants screened by the initial email/phone contact will be determined).

The reason we are looking at individuals with overweight and obesity exclusively (Inclusion A), is because we are targeting individuals at high risk for cardiometabolic diseases, such as type 2 diabetes and cardiovascular disease with the purpose of disease prevention. The reason for inclusion criteria B-D is those factors have been shown to impact weight, and therefore could be potential confounders. Due to the two required visits to the lab (i.e., pre- and post- intervention), we need participants who are local (Inclusion E). Since we will be measuring body composition with a BIA device, these individuals will not be able to partake (Inclusion F).

7.6. List all study specific the exclusion/ineligibility criteria. The exclusion criteria must parallel the inclusion criteria:

- A) Adolescents (age <14 years old and/or sex- and race-specific BMI percentile <85th) and adults with normal weight or overweight adults (Age >30 years old and/or BMI <25 kg/m²) will be excluded in the study.
- B) Have at least one of the following chronic medical conditions: heart disease, arrhythmias, diabetes, thyroid disease, bleeding disorder, history of pulmonary disease, hypertension, hepatorenal disease, musculoskeletal disorder, neuromuscular/neurological disease, autoimmune disease, cancer, peptic ulcers, anemia, or chronic infection (HIV).
- C) Have taken any of the following medications: heart, pulmonary, thyroid, anti-hyperlipidemic, hypoglycemic, anti- hypertensive, endocrinologic (e.g., thyroid, insulin, etc.), emotional/psychotropic (e.g., Prednisone, Ritalin, Adderall), neuromuscular/neurological, or androgenic medications (anabolic steroids).
- D) Does not live in the greater Syracuse area.
- E) Has a pacemaker.
- F) For females: are not pregnant or lactating.

We will explain details of the health conditions for the participants to make sure they understand each health condition completely. We will also examine their body composition and blood glucose before we determine whether they are qualified to participate in the study. During the study, if participants have concerns regarding their health conditions, they are free to refuse to participate, or to withdraw from the study at any time. If there is concern about their medical safety, we may recommend participants seek medical attention.

Exclusion criteria will be monitored by [name] [name] and [name], when they contact him and communicate about the study procedure via email and/or phone.

7.7. Does this research involve participants likely to be vulnerable to coercion or undue influence?

- No. (Skip to 7.8)**
- Yes. If yes, describe the additional protections included in the protocol to protect their rights and welfare.**

7.8. General state of Health: ("Unknown" - unless you will obtain health data on participants prior to beginning the study.)

As we indicated in the inclusion criteria, this study will recruit adolescents (age 14-17 years old with sex- and race-specific BMI percentile $\geq 85^{\text{th}}$) and young adults with overweight and obesity (age 18 to 30 years old with BMI $\geq 25 \text{ kg/m}^2$). Therefore, general state of health of all participants will be weight status (normal weight, overweight, obese) determined by age and BMI obtained prior to beginning the study (when we check participants' eligibility).

8. Recruitment of Participants

8.1. Describe in detail how participants will be identified and recruited. Include in your description how you will have access to a population that will allow recruitment for the number of participants required for your research. Do not merely state "Volunteers".

The study population will consist of individuals recruited from Syracuse University, other local colleges/universities as well as individuals in the local communities. Participants will be recruited via paper flyers and social media postings. Flyers will also be attached to departmental research boards around the Syracuse campus. If participants are interested in our study after seeing the flyer, they will contact us at the e-mail provided in the flyer. If participants are interested in the study after seeing the social media (CRL and HPL official Instagram accounts) post, they will contact us at the e-mail provided in the post. The flyers will be used for the social media post. The script for recruitment is as follows:

“Dear (name),

My name is [name], and I am a doctoral student in the department of Exercise Science at Syracuse University. I am emailing you regarding your potential interest in our research study.

We are interested in how time restricted eating and high intensity interval training will impact the metabolic health of individuals under the age of 31, with a body mass index of 25 or higher. We will have one group randomly assigned into a group that only eats during a ten-hour window per day, one group that performs a high intensity interval training 20-minute workout three times per week, one group that does both, and one group that does neither. This study will last for four weeks. Before the intervention starts, and after the intervention is completed, we will ask you to come to the Clinical Research Lab (third floor of the Women's Building, room 303), where we will assess your height, weight, body composition. Then we will escort you to SUNY Upstate for a two-hour oral glucose tolerance test, where you will have your blood drawn every 30-minutes. Each of these two lab visits will take about three hours to complete. After each lab visit is finished, you will be compensated via Amazon gift cards.

If this still sounds like something you would be interested in, or if you have any additional questions, you can email me back or call me on the [contact]. I have attached the consent form to this email as well, so this way you can look it over at your leisure.

Thank you for your time and potential interest in our study.”

8.2. Describe who will recruit participants.

[name] will recruit participants.

8.3. Identify all applicable recruitment methods that apply: NOTE:Copies of all advertising materials including flyers, posters, ads, letters, scripts or detailed descriptions; including graphics **MUST be provided with your application. (See [SOP 036 for Recruitment/Advertising](#)).**

Flyers

E-mail

SU Today News Service

- Internet Posting
- Letter
- Telephone
- Other (describe): _____

- Posters
- Newspaper
- Radio

- Television
- Departmental Research Boards
- Social Media

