and reconstructs it into a pressure wave. From this wave, we can estimate blood pressure in this artery and calculate the stiffness (or how elastic the artery is). This measure takes 5-minutes to complete.

C) Randomization:

Upon completion of the Pre-Intervention Lab Visit, participants will be randomly assigned into one of three groups: (a) TRE, (b) HIIT, and (c) Control. The randomization will be done separately for adolescents and young adults [with the exploratory purpose of future analysis on age-specific difference in interventional effects on cardiometabolic health]. Within each group, we anticipate that there will be an equal number of adolescents and young adults.

(a) Time Restricted Eating (TRE) trial:

Participants randomized into the TRE group will be instructed to consume all their calories within a 10-hour period. We will instruct participants that they can choose their time-window (early TRE [7am – 5pm] or late TRE [1pm – 11pm]), but it must remain constant for the duration of the study. Further, we will give no restrictions on the type of foods and/or the quantities individuals can consume. We will ask individuals to maintain their diet for the duration of the study. Participants will be given clear instructions on their diet and how to use the “MyFitnessPal” application. Participants will have their total daily energy requirement calculated using the following formula (Basal metabolic rate [BMR] x activity level) and will be told to eat that amount within their allotted time window. BMR will be calculated when participants have their body composition taken by the InBody. Participants will be told to start their 4-week diet the following day after visit.

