The InBody only possess a risk for individuals with a pacemaker. However, if individuals have a pacemaker, they will not be eligible for this study since that is one of the exclusion criteria.

The blood pressure cuff possesses only a slight risk of causing mild discomfort for the participant. However, we will thoroughly instruct the participants of the procedure and let them know the cuff will not be on their arm for long.

Trained nurses at SUNY Upstate will administer the oral glucose tolerance test and draw blood from the participants. The area will be cleaned and disinfected prior to collection of blood. After the blood draw is complete, participants will be handed a sterile gauze and a band-aid to minimize risk of infection. Furthermore, participants will be in a phlebotomy chair with a protective bench in front, in case they may become faint. If this does occur, the blood draw will cease immediately.

Participants will be instructed to have enough warm-up stretching and to do workout within their limit to minimize potential risks associated with HIIT (e.g., muscle soreness, cramping). In order to minimize potential risk associated with TRE (e.g., light-headedness, hunger), participants will be instructed to drink water as needed.

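### The closed condition lists in 7.5 B and 7.6 B name no eating disorder, although one arm, open to 14-17-year-olds, is four weeks of restricted eating hours with food tracking

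*Protocol*

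**What the plan says.** Section 7.5 is meant to hold all inclusion criteria. Item B opens "Free from the following chronic medical conditions: heart disease, arrhythmias, diabetes, thyroid disease, bleeding disorder, history of pulmonary disease, hypertension, hepatorenal disease" and continues "musculoskeletal disorder, neuromuscular/neurological disease, autoimmune disease, cancer, peptic ulcers, anemia, or chronic infection (HIV"). Section 7.6 B mirrors it: "Have at least one of the following chronic medical conditions: heart disease, arrhythmias, diabetes, thyroid disease, bleeding disorder" and so on through the same list. Neither list has a catch-all clause.

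Two other criteria bear on the point. Item A sets age and weight: "Adolescents (age 14-17 years old with sex- and race-specific BMI percentile" at or above the 85th, or age 18-30 with BMI of at least 25 kg/m². Item C bars anyone who has taken certain drugs, including "emotional/psychotropic (e.g., Prednisone, Ritalin, Adderall").

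On screening, 7.5 and 7.6 say eligibility is monitored through email or phone contact, together with body composition and (in 7.6) blood glucose. Section 7.5 adds that no physician is consulted at the initial visit.

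On exposure, section 4.1 C(a) has TRE participants "instructed to consume all their calories within a 10-hour period", gives them a calculated daily energy amount and instructs them in a food-tracking app. Section 8.4.2 pays the TRE arm per day for a home-based food-tracking survey. On risk, 12.1 names light-headedness and hunger as examples for TRE, and 12.2 answers: "In order to minimize potential risk associated with TRE (e.g., light-headedness, hunger), participants will be instructed to drink water as needed".

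**The concern.** Eligibility is the protocol's main tool for keeping people out of an arm that may not suit them. The TRE arm consists of rules about when to eat, an energy figure and tracking of food. It is plausible that this could harm a participant with an eating disorder, and the trial recruits minors. If the lists are applied as written, a 14-17-year-old with a current eating disorder who has never taken a listed drug meets every criterion and can be randomised to TRE. The same holds for participants aged 18-30.

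The protocol's own reasoning points towards covering this. The rationale in 7.5 justifies the condition and medication criteria as factors shown to affect weight. Pacemakers are excluded because of the risk from a body-composition measurement lasting about a minute. No criterion is stated as a control on the risk of four weeks of TRE.

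**Working it through.** The protocol gives no figure to reproduce here. The check sets the criteria against the exposure and then sizes the exposure.

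**1. Is the condition covered?**

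| Safeguard | Where | What it covers |
|---|---|---|
| Condition list | 7.5 B, 7.6 B | 15 named conditions; no eating disorder and no psychiatric condition |
| BMI threshold | 7.5 A | Rules out low-weight eating disorders; leaves those at or above the threshold |
| Drug history | 7.5 C, 7.6 C | No time limit, so past psychotropic use counts; misses untreated cases and those treated without drugs |
| Screening contact | 7.5, 7.6 | Asks about the listed conditions; eating behaviour is not mentioned |
| Measurements | 7.5, 7.6 | Body composition and blood glucose; neither is described as a check on eating behaviour |
| Physician review | 7.5 | None at the initial visit |
| TRE mitigation | 12.2 | Drinking water |

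What remains is anyone at or above the BMI threshold with an eating disorder not treated with a listed drug.

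**2. Who is exposed, and to what?**

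- Allocation (4.1): 20 + 20 + 10 = 50, so the TRE share is 20/50 = 40%.
- Adolescents in TRE: 4.1 C expects equal numbers of adolescents and young adults in each group, so 20/2 = 10.
- Daily time without calories: 24 - 10 = 14 h, for four weeks.
- Tracking frequency: 8.4.2 pays $3 per day in one week and $4 per day in the next. 7 × $3 + 7 × $4 = $49 per two weeks, close to the $50 instalment in 8.4.1. This fits tracking on every day, though no section states a daily duty outright.

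**3. How many might be affected?** The protocol gives no frequency. Suppose a proportion p of those who pass the present criteria have an eating disorder, with p between 2% and 10% taken only for illustration. The expected number is n × p, and the chance of at least one is 1 - (1 - p)^n.

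| Assumed p | Expected in TRE (n = 20) | At least one of 20 | At least one of 10 adolescents |
|---|---|---|---|
| 2% | 0.4 | 33.2% | 18.3% |
| 5% | 1.0 | 64.2% | 40.1% |
| 10% | 2.0 | 87.8% | 65.1% |

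These figures restate the assumption. They show only that, if the condition is not very rare among those eligible, an arm of 20 could well include someone affected.

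**The case against.** The strongest reply is that nothing here is a contradiction or a wrong number. That eating disorders matter for TRE is a clinical judgement the protocol does not make. This stands, and it limits the point to an improvement in the criteria.

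The exposure is also milder than a bare 14-hour fast suggests. The participant chooses an early or late window, and the fast includes the night. All arms fast 10-12 hours before each test visit, so the difference from that is 14 - 12 = 2 to 14 - 10 = 4 hours, although repeated daily. The energy figure is a calculated requirement (basal rate times activity level), not a deficit, and 4.1 C(a) sets no limit on types or quantities of food. The risks in 12.1 are given as examples, so it cannot be said that the protocol claims there are no others.

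Criteria A and C narrow the gap, and minors need parental consent as well as their own assent. The consent and assent pages are not available for this review and may carry a warning. A warning would still not be an eligibility criterion.

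Two stronger readings are tempting. A reader might infer that people with eating disorders are those TRE would harm most; the protocol neither ranks nor quantifies harm, so only plausible harm can be claimed. A reader might also infer that disordered eating would bias the TRE comparison through adherence, food records or withdrawal; nothing in the protocol supports an effect of that kind or its size.

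**Conclusion.** The omission is real, and it is fixed in the protocol rather than left to an analysis plan. Both closed lists leave out eating disorders, the other criteria cover them only in part, and the screening described would not be expected to find the remaining cases. A minor with an eating disorder not treated with drugs can be enrolled and assigned to TRE under the plan as written.

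The exposed group is 20 of 50 participants, about 10 of them aged 14-17 if the anticipated age split is met. The number actually affected is unknown, and any prevalence used is an assumption. The conclusion rests on one clinical premise from outside the protocol: that restricted eating hours with food tracking could plausibly harm someone with an eating disorder. It is a cheap safety improvement, not a demonstrated error in the design or a threat to the trial's validity.

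**What to change.** The investigator and IRB should:

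- add eating-disorder history to the condition lists in 7.5 B and 7.6 B, deciding themselves how to define it (current, past or both);
- ask about it in the existing eligibility contact, before randomisation and for all three arms so that the groups remain comparable, with the parent involved for ages 14-17;
- mention it among the TRE risks in 12.1 and 12.2.

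The cost is one item in two lists, one screening question and a line in the risk section. The downside is that a few otherwise eligible people are excluded.

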8.4. Will participants be compensated?

- No. (Skip to Section 9)
- Yes. If yes, answer 8.4.1. and 8.4.2. below.

Note: All information regarding compensation must be included in consent/assent documents.

8.4.1. If Yes, specify the method of compensation (e.g. monetary, course credit, gift card, toy, etc.), the amount of compensation, and how the compensation will be awarded (per task, per session, etc.).

Compensation will be given out after each visit via Amazon gift cards.

50 dollars will be given out after completion of visit one (pre-intervention visit).

50 dollars will be given out after participants complete the first two weeks of the intervention (with the exception of control group).

50 dollars will be given out after participants complete the last two weeks of the intervention (with the exception of control group).

50 dollars will be given out after completion of visit two (post-intervention visit).

In total, 200 dollars will be given out for participants who complete the study protocol. Participants in the Control will obtain 100 dollars upon their completion of the visits.

8.4.2. Describe how compensation will be awarded if the participant withdraws after beginning the study. Compensation cannot be contingent upon full participation and must be pro-rated in a manner that recognizes the time and effort of the participant prior to withdrawal. Provide a copy of the pro-rating schedule.

For the intervention group, there will be four time points for participants receiving compensation. The first and last compensation will be for the time and effort of one-time visit (i.e., one-day measurement visit). If participants come to the lab but are not able to complete all tasks or measurements during the visit, they will receive \$10 for their time and effort for the visit. The second and third compensation will require 2 weeks of intervention. Each compensation will be provided based on their time and effort with the pro-rating schedule below.

[HIIT intervention: lab visit] 1st week of intervention: \$8/day; 2nd week of intervention: \$9/day; 3rd week of intervention: \$8/day; 4th week of intervention: \$9/day

[TRE intervention: home-based food track survey] 1st week of intervention: \$3/day; 2nd week of intervention: \$4/day; 3rd week of intervention: \$3/day; 4th week of intervention: \$4/day

For the control group, the compensation will be given based on their one time visit so pro-rating schedule will not be applicable.

9. Informed Consent Procedures

Consent is required for all human subject participants. Final copies of ALL consent/assent documents (including electronic or oral scripts) must be provided for IRB approval and date stamping. Informed consent/assent documents must be on *official SU departmental letterhead*.

Must use NEW consent form templates as indicated for the type of consent you plan to use.

9.1. How many consent documents are included with this application? 2

9.2. How many assent documents are included with this application? 1

